#### **1.3.1. Known and Potential Benefits and Risks of the Test Investigational Medicinal Product(s)**

Results from Phase 2b clinical studies have demonstrated statistically significant reductions in mean headache hours after 1, 2, and 3 months of sc fremanezumab treatment in patients with chronic migraine and statistically significant reductions in monthly migraine days after 1, 2, and 3 months of fremanezumab treatment in patients with episodic migraine. Results for several secondary/exploratory endpoints also showed fremanezumab to be superior to placebo.

Fremanezumab has generally been well tolerated over the ranges of doses evaluated (single iv infusions at 0.02 to 2000 mg in healthy subjects, multiple iv infusions at 30 to 300 mg in healthy subjects, and multiple sc doses at 225 to 900 mg in healthy subjects and migraine patients). The most common treatment-emergent adverse events across all patients/subjects studied were mild to moderate transient general administration site disorders/reactions. Other commonly reported treatment-emergent adverse events were headache, back pain, and upper respiratory tract infection.

Reports of mild to moderate transient administration site disorders/reactions, including injection site bruising, injection site swelling, administration site pain, injection site pain, injection site pruritus, injection site dermatitis, injection site rash, injection site edema, injection site discomfort, injection site hemorrhage, injection site irritation, injection site mass, and injection site hematoma, have occurred with sc administration. In addition, reports of mild and transient infusion site pain and swelling following iv administration have occurred. Among these events, the following have been identified as adverse drug reactions (identified risks): injection site erythema, administration site pain, injection site pain, injection site pruritus, and injection site dermatitis. None of these identified risks are considered important risks.

Infusion-related reaction and drug hypersensitivity were also identified as adverse drug reactions. To date, 1 subject who received fremanezumab iv had a non-serious infusion-related reaction, and 1 patient who received fremanezumab via the sc route had a non-serious event of drug hypersensitivity. Both events resolved following IMP discontinuation and treatment with diphenhydramine and methylprednisolone. Neither of these identified risks are considered important risks.

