**Figure 1: Overall Study Schematic Diagram**

CCH=chronic cluster headache; IV=intravenous; PBO=placebo; SC=subcutaneous; V=visit.

Note: Patients randomized to the 900-mg iv loading dose group will receive 900 mg of fremanezumab administered via an approximately 1-hour iv infusion followed by 3 placebo sc injections at visit 2 (week 0) and fremanezumab at 225 mg administered as single sc injections at visits 3 and 4 (weeks 4 and 8, respectively). Patients randomized to the 675-mg sc loading dose group will receive placebo administered via an approximately 1-hour iv infusion and fremanezumab at 675 mg administered as 3 sc injections (225 mg/1.5 mL) at visit 2 (week 0) and fremanezumab at 225 mg administered as single sc injections at visits 3 and 4 (weeks 4 and 8, respectively). Patients randomized to the placebo group will receive placebo as an approximately 1-hour iv infusion followed by placebo administered as 3 placebo sc injections at visit 2 (week 0) and placebo as single sc injections at visits 3 and 4 (weeks 4 and 8, respectively).

**Wearable Sensor Substudy:** A subset of patients in selected investigational sites will be offered the opportunity to participate in a substudy to understand the utility of physiological biomarker measures captured through wearable digital sensor devices as tools to monitor response to treatment and disease symptoms (eg, activity/sleep disruption). Refer to Section 8.6 for additional details.

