z Injection site will be assessed for erythema, induration, ecchymosis, and pain immediately (+10 minutes) and 1 hour (±15 minutes) after IMP administration. If a patient has severe injection site induration, erythema, ecchymosis, or pain at 1 hour after completion of IMP administration, the patient will be reassessed 3 hours (±15 minutes) after completion of IMP administration and hourly (±15 minutes) thereafter until the reaction is of moderate or less severity.

ADA=antidrug antibody; β-HCG=beta-human chorionic gonadotropin; CH=cluster headache; CRF=case report form; ECG=electrocardiogram; eC-SSRS=electronic Columbia Suicide Severity Rating Scale; EOT=end of treatment; EQ-5D=EuroQol-5 Dimension; FSH=follicle-stimulating hormone; HADS=Hospital Anxiety and Depression Scale; IMP=investigational medicinal product; iv=intravenous; PGIC=Patients' Global Impression of Change; PPSI=Patient-Perceived Satisfactory Improvement; RNA=ribonucleic acid; sc=subcutaneous; SF-12=12-Item Short Form Health Survey; V=visit; WPAI=Work Performance and Activity Impairment.

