#### **5.1.1.1. Starting Dose and Dose Levels**

Patients randomized to receive fremanezumab will receive either 900 mg or 675 mg. At visit 2 (week 0), iv administration of treatment (IMP or placebo) will precede sc administration (IMP or placebo). Patients randomized to the 900-mg iv loading dose group will receive 900 mg of fremanezumab as an approximately 1-hour iv infusion followed by 3 placebo sc injections at visit 2 (week 0) and fremanezumab at 225 mg administered as single sc injections (225 mg/1.5 mL) at visits 3 and 4 (weeks 4 and 8, respectively). Patients in the 675-mg sc dose group will receive placebo as an approximately 1-hour iv infusion followed by fremanezumab at 675 mg administered as 3 sc injections (225 mg/1.5 mL) at visit 2 (week 0) and fremanezumab at 225 mg administered as single sc injections at visits 3 and 4 (weeks 4 and 8, respectively).

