### 7.11. Injection Site Assessments

Injection site assessments will be performed immediately (+10 minutes) and 1 hour ( $\pm 15$  minutes) after receiving each dose of the IMP. The injection site(s) will be assessed for erythema, induration, and ecchymosis.

Severity will be graded according to the following criteria:

- Injection site erythema, induration, and ecchymosis will be graded according to measurements: absent, 5 to  $\leq 50$  mm (mild),  $>50$  to  $\leq 100$  mm (moderate), and  $>100$  mm (severe). Induration must be assessed by careful superficial palpation avoiding pressuring or squeezing the injection site.
- For spontaneous report of local pain after the injection, it will be measured as summarized in Table 5.

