#### **Visit 2 (Week 0 [Day 0+3 Days])**

After completing predose assessments, patients will be treated with IMP. Refer to Section 5.1.1 for details regarding IMP administration. A 4-mL blood sample for pharmacokinetics analysis will be collected at the end of the IMP infusion (+10 minutes) from the arm that is not used for the IMP infusion.

The following procedures and assessments will be performed at visit 2 (week 0) after dosing:

- Perform local injection site assessment immediately (+10 minutes) and at 1 hour ( $\pm 15$  min) after completing IMP administration. Additional injection site assessments may be performed based on the severity of any observed injection site reaction. See Section 7.11 for additional details.
- Evaluate for anaphylaxis and hypersensitivity reaction.
- Inquire about postdose adverse events before the patient leaves the study center.

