8.3. Adverse Events

Adverse events will be recorded from time informed consent is obtained through the end of study participation.

The following are considered protocol-defined adverse events of special interest to be sent to the sponsor's Global Patient Safety and Pharmacovigilance Department for evaluation: ophthalmic-related adverse events of at least moderate severity, events of possible drug-induced liver injury (aspartate aminotransferase or alanine aminotransferase $\geq 3 \times$ the upper limit of normal [ULN], total bilirubin $\geq 2 \times$ the ULN, or international normalized ratio >1.5), Hy's Law events, or events of anaphylaxis and severe hypersensitivity reactions.

All adverse events will be coded using MedDRA (version 18.1). Each patient will be counted only once in each preferred term or SOC category for the analyses of safety. Summaries will be presented for all adverse events (overall and by severity), adverse events determined by the investigator to be related to test IMP (defined as related or with missing relationship) (overall and by severity), serious adverse events, and adverse events causing withdrawal from the study. Adverse events with the missing flag indicating serious will be excluded from the summary of serious adverse events but included in the summary of non-serious adverse events.

Summaries for injection site and infusion-related adverse events and protocol-defined adverse events of special interest will be presented (overall and by severity).

Listings for deaths, serious adverse events, adverse events leading to discontinuation, injection site and infusion-related adverse events, and protocol-defined adverse events of special interest will be presented. In addition, listings for MedDRA dictionary terms for adverse event descriptions and adverse event preferred terms by patient number and treatment group will be presented.

Spontaneous abortion or an elective abortion due to developmental anomalies will be reported as a serious adverse event (protocol Section 7.2). These serious adverse events will be listed separately if applicable.

Summaries will include treatment-emergent adverse events which are defined as adverse events occurring at or after the first dose of the IMP. The listing will include all adverse events recorded.

Adverse events for patients who did not meet screening criteria will be listed.

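### At visit 2 the scheduled graded local examination omits the infusion site, so local reactions to the iv and sc loading doses are not ascertained or graded alike

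*Protocol*

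**What the plan says.** Four places describe the scheduled local examination, and each names the injection site.

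- Protocol Section 7.11: "The injection site(s) will be assessed for erythema, induration, and ecchymosis", to be done "after receiving each dose of the IMP". Erythema, induration and ecchymosis are measured in millimetres. Pain, when spontaneously reported, is graded with Table 5.
- Protocol Table 2, footnote z: "Injection site will be assessed for erythema, induration, ecchymosis, and pain immediately (+10 minutes) and 1 hour (±15 minutes) after IMP administration".
- Protocol Appendix B, visit 2, after dosing: "Perform local injection site assessment immediately (+10 minutes) and at 1 hour".
- SAP Section 8.4 repeats the Section 7.11 list and sends injection-site reactions to the adverse event summaries.

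On dosing, the note to Protocol Figure 1 says that the iv arm receives "900 mg of fremanezumab administered via an approximately 1-hour iv infusion followed by 3 placebo sc injections at visit 2 (week 0"). Section 5.1.1.1 agrees: "as an approximately 1-hour iv infusion followed by 3 placebo sc injections at visit 2 (week 0").

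On background, Protocol Section 1.3.1 states that "reports of mild and transient infusion site pain and swelling following iv administration have occurred".

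On reporting, SAP Section 8.3 says: "Summaries for injection site and infusion-related adverse events and protocol-defined adverse events of special interest will be presented (overall and by severity").

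**The concern.** The double-dummy design puts the active loading dose at a different site in each active arm. The scheduled examination follows the sc sites only. In the sc arm it looks at the three places where active drug went in. In the iv arm it looks at three placebo sites, and the one site that received the loading dose has no scheduled, graded examination. The protocol itself reports infusion-site pain and swelling with this drug, so there is something to look for.

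At stake is the description of local tolerability by route. Protocol Section 5.3.1 says that the two forms of loading dose are there to provide data on the benefit of either route. A reader of the adverse event tables will naturally set the iv column beside the sc column. If reactions in one column come partly from two scheduled measurements and those in the other come from general inquiry, a difference between the columns may reflect how the reactions were sought.

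**Working it through.** No power or sample-size formula applies. The check is a reading of the text plus a count of sites.

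**1. Could the term injection site include the infusion site?** Section 7.11 does not expressly exclude it, and a site could read the reference to each dose broadly. The documents otherwise keep the terms apart:
- Section 3.1 counts infusions and injections separately.
- Section 1.3.1 separates injection-site from infusion-site reactions.
- Section 5.1 records the number and location of sc injections only.
- SAP Section 8.3 names injection-site and infusion-related events as two kinds.

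No schedule row, procedure list or grading scale names the infusion site. The narrow reading is an inference, but a well-supported one.

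**2. Where the active drug goes at visit 2.** Inputs are Appendix G (4 syringes of 225 mg in the infusion bag), Section 5.1.1.1 and Section 5.1.2. Every patient has 1 infusion site + 3 sc sites = 4 sites.

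| Arm | Active drug by infusion | Active drug in the 3 sc sites | Examined sites with active drug |
|---|---|---|---|
| 900-mg iv | 4 × 225 = 900 mg | 0 mg | 0 of 3 |
| 675-mg sc | 0 mg | 3 × 225 = 675 mg | 3 of 3 |
| Placebo | 0 mg | 0 mg | 0 of 3 |

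On the structured examination at visit 2 the iv arm looks exactly like placebo.

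**3. Whole study.** Visits 3 and 4 add one sc site each, active in both fremanezumab arms and examined in both. Examined sites with active drug: iv arm 0 + 1 + 1 = 2 of 5; sc arm 3 + 1 + 1 = 5 of 5. The gap is confined to visit 2.

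**4. How a local reaction to the loading dose reaches the tables.**

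| | sc loading dose | iv loading dose |
|---|---|---|
| Scheduled examination | Immediately and at 1 hour | None |
| Adverse event inquiry and observed signs (Table 2 footnote g, Section 7.1.2) | Yes | Yes |
| Severity scale | Section 7.11 measurements and Table 5 | General scale, Section 7.1.3 |

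Section 7.11 says that injection-site reactions should be recorded as adverse events, so the scheduled findings feed the SAP Section 8.3 summaries. Section 7.1.3 refers only injection-site erythema, induration, ecchymosis and pain to the Section 7.11 scale. An infusion-site reaction therefore falls to the general scale, which rests on limitation of usual activities. For example, erythema wider than 100 mm that limits nothing is severe at an sc site and mild at the infusion site. SAP Section 8.3 presents these events by severity, so the difference in scale carries into the output.

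**5. Which signs are affected most.** Section 7.11 grades sc pain on spontaneous report, although footnote z lists pain among the scheduled items. For pain the contrast between routes is therefore weaker. It is clearest for erythema, induration and ecchymosis.

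**The case against.** The strongest reply has four parts.

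**Collection is not missing.** A reader might infer that infusion-site reactions reach the data only if the patient volunteers them. The documents do not support that. Adverse events are asked about before and after dosing, with the post-dose inquiry made before the patient leaves (Table 2 footnote g, Appendix B). Section 7.1.2 requires questioning at each contact and the recording of observed as well as reported signs. Section 5.5.1 keeps patients on site for at least 60 minutes after the infusion, subject to medical judgment. This part stands: what is missing is scheduled, graded examination.

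**The planned contrasts are against placebo.** A reader might infer that the design favours the iv regimen by construction. The stated hypotheses (Protocol Section 9.6, SAP Section 7) compare each active arm with placebo, and safety is descriptive. All arms receive an infusion and three sc injections under blind, so infusion-site events are sought in the same way in the iv and placebo arms. This also stands. It does not reach the side-by-side reading of the two active columns, which the tables invite.

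**The choice of sites is defensible.** Section 1.3.1 calls the infusion-site events mild and transient, and does not name infusion-site pain or swelling among the identified adverse drug reactions. The iv-specific identified reaction, infusion-related reaction, is addressed by the hypersensitivity check during and after dosing. This limits the importance of the point, but that check is not an inspection of the local site.

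**The counts are not an effect size.** Finding 0 of 3 against 3 of 3 describes coverage, and no expected reaction rate is given. This is correct. The Section 7.11 scale also omits swelling, and redness or bruising can come from the cannula alone, so any fix must deal with both.

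**Conclusion.** The point holds as a minor design gap. At visit 2 the site that received the iv arm's loading dose has no scheduled graded examination, while all three sites that received the sc arm's loading dose do. Local reactions to the two loading doses therefore differ in ascertainment and in severity grading, and a descriptive iv-versus-sc comparison of local tolerability is not like for like.

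The likely direction is relative under-counting for the iv loading dose, because a scheduled examination tends to find more than general inquiry. The documents give no reaction rates, so the amount cannot be derived.

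The conclusion rests on reading injection site as excluding the infusion site. If the sponsor intended the wider meaning, the remaining fault is that none of the four places says so.

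**What to change.** In Protocol Section 7.11, Table 2 footnote z and Appendix B, add inspection of the infusion site in all three arms at the two existing visit-2 time points. Use the Section 7.11 measurements for erythema, induration and ecchymosis, add swelling with a stated scale, and use the Table 5 grades for pain. Extend the cross-reference in Section 7.1.3 so that infusion-site reactions are graded in the same way.

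In SAP Sections 8.3 and 8.4, summarise infusion-site and injection-site reactions separately by arm, with the placebo arm's infusion site as the reference for cannulation effects.

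Every patient has an infusion, so the blind is kept, and staff are already examining injection sites at those times. The cost is one more site to record at visit 2 and one more table. If data collection can no longer change, the separate tables are still possible, with a note that the two kinds of site were ascertained and graded differently.

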**Table 5: Severity of Pain Scale for Injection Site Assessments**

Symptom	Severity grade	Assessment
Pain	0	Absent
	1	Mild
	2	Moderate
	3	Severe

If a patient has severe injection site induration, erythema, ecchymosis, or pain at 1 hour after completion of IMP administration, the patient will be reassessed at 3 hours ( $\pm 15$  minutes) after completion of IMP administration and hourly ( $\pm 15$  minutes) thereafter until the reaction is of moderate or less severity.

Appropriate treatment may be provided if necessary, in which case it must be recorded as concomitant medication.

Injection-site reactions (injection site erythema, induration, ecchymosis, and pain) should be recorded as adverse events.

## **8. ASSESSMENT OF PHARMACOKINETICS/BIOMARKERS/PHARMACOGENOMIC/IMMUNOGENICITY/ANCILLARY STUDIES**

### **8.1. Pharmacokinetics Assessment**

Sampling for pharmacokinetics will be sparse. Thus, the fremanezumab pharmacokinetics samples will be analyzed using a population pharmacokinetics approach and will be reported separately to the clinical study report.

Blood samples (4 mL) will be collected via venipuncture/indwelling catheter at the time points detailed in [Table 2](#) for plasma concentration measurements of fremanezumab. The dates and times of IMP administration and the date and time of each pharmacokinetics sample will be recorded on the source documentation and transcribed onto the CRF.

Samples from patients who receive active IMP will be analyzed for concentration of fremanezumab using a validated method. Samples from patients who were randomized to receive placebo will not be analyzed. Details on sample handling, storage, shipment, and analysis are given in [Appendix N](#).

### **8.2. Pharmacodynamics Assessment**

Pharmacodynamics parameters are not evaluated in this study.

### **8.3. Immunogenicity Testing**

Blood samples (5 mL) will be collected via venipuncture or indwelling catheter at the time points detailed in [Table 2](#) for immunogenicity testing.

Samples from patients who receive active IMP will be analyzed for ADA using a validated method. Samples from patients who receive placebo will not be analyzed unless the patient elects to enroll into an available extension study where the patient will receive fremanezumab treatment. In this case, the pre-dose (baseline) sample from the rolled-over placebo patient will be analyzed along with post-treatment samples collected in the extension study and values will be reported in the extension study. Details on sample handling, storage, shipment, and analysis are provided in [Appendix O](#).

### **8.4. Assessment of Exploratory Biomarkers**

Biomarkers are defined as biological substances that monitor physiological effects, assess drug activity, and predict clinical outcome, safety, and response to therapy. Details on sample handling, storage, shipment, and analysis are provided in [Appendix P](#).

CGRP-containing nerve fibers are prevalent in bone tissue and have been hypothesized to be important in the regulation of bone metabolism, response to bone injury, and the perception of bone pain. In vitro, CGRP is anabolic to osteoblasts and can inhibit maturation to osteoclasts. Preclinical studies suggest CGRP antagonism may have benefit in osteoarthritis ([Benschop et al 2014](#)) and bone-related pain. In the current study, exploratory analysis may be conducted on

blood (serum, plasma, and ribonucleic acid [RNA]) and urine biomarkers for extracellular matrix turnover, bone formation, and bone resorption.

In preclinical models, CGRP can promote angiogenesis in ischemia, capsaicin-induced synovitis, and neovascularization of tumors. Exploratory analysis will be conducted on endothelial/angiogenic markers to determine if fremanezumab alters angiogenic markers.

CGRP is known to act directly on macrophage and dendritic cells by inhibiting them from producing inflammatory cytokines and presenting antigens to T cells. It has been hypothesized that CGRP may act as a regulator of the innate immune response. Exploratory analysis will be conducted on inflammatory endpoints in blood to examine effects of fremanezumab in patients with CH.

Based on the known biology of CGRP's mechanism of action, biomarker assessment will potentially include markers of bone remodeling, inflammation, and angiogenesis. The validated multiplex immunoassay panels will be applied to measure changes in urine, serum, plasma, and RNA biomarkers.

The planned biomarker analysis will be detailed in a separate document, which may be updated at a later stage before the analysis to allow updating with new scientific information.

## **8.5. Pharmacogenomics**

For information regarding pharmacogenomics assessments, see [Appendix Q](#). Multiple genetic loci have been identified that could affect the binding affinity of the CGRP-receptor-ligand complex, while other genetic loci have been identified as having roles in migraine and/or headache onset ([Anttila et al 2013](#)). To explore the potential impact of normal variations in these loci on parameters in this study, a blood sample (6 mL) will be collected from each patient (unless the patient declines testing or local regulations prohibit testing) for pharmacogenomic assessment during this study. Pharmacogenomic assessment potentially includes the association analysis of both known and unknown DNA and RNA genetic variations.

